This proposal includes experiments designed to achieve both mechanistic insight and demonstration of therapeutic principle. CES is innovative: the delivery patterns, configurations, and subject population proposed here are novel. CES is practical: non-invasive stimulation carries significantly lower cost, lower risk, and greater ability to widely implement than surgically implanted stimulation, especially at the cervical level. Unlike TMS, surface electrical stimulation may be easily combined with simultaneous physical exercise. This approach is broadly applicable: it could be used for individuals with other neurological injuries such as stroke, spinal cord injury, multiple sclerosis, or traumatic brain injury. Finally, CES is compatible: it could be combined with drug or cell-based treatments to hopefully produce synergistic functional benefits in the future.

Please note that this IRB application involves similar neural stimulation procedures as already reviewed and approved in study HAR-15-001, HAR-16-042, and HAR-17-017. This application directly parallels the protocol of HAR-17-017, but in a different subject population and funded by a different agency, requiring separate IRB applications.

3. PROCEDURES, METHODS AND EXPERIMENTAL DESIGN.

Participants: Ages between 21 and 75. n=24 subjects with ALS. n=27 non-disabled volunteers.

Inclusion criteria

Non-disabled participants

1. Age between 21 and 75 years; n=15 for Aim 1, n=12 for Aim 2;
2. No known central or peripheral neurological disease or injury.

ALS participants

1. Age between 21 and 75 years; n=12 for Aims 1 and 2;
2. Diagnosis of definite or probable ALS by Escorial Criteria;
3. Weakness (not paralysis) or either hand: Score of 2, 3, or 4 (out of 5) on manual muscle testing of wrist extension, wrist flexion, finger extension, finger flexion, or finger abduction in left or right hand;

Exclusion criteria

1. History of other serious injury or disease of central or peripheral nervous system;
2. History of seizures;
3. Ventilator dependence or patent tracheostomy site;
4. Use of medications that significantly lower seizure threshold;
5. History of head trauma with evidence of brain contusion or hemorrhage or depressed skull fracture on prior imaging;
6. History of implanted brain/spine/nerve stimulators, aneurysm clips, ferromagnetic metallic implants, or cardiac pacemaker/defibrillator;
7. Significant coronary artery or cardiac conduction disease;

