8. History of bipolar disorder or suicide attempt or active psychosis;
9. Heavy alcohol consumption (> equivalent of 5 oz of liquor) within previous 48 hours;
10. Open skin lesions over the face, neck, shoulders, or arms;
11. Pregnancy;
12. Unsuitable for study participation as determined by study physician

Recruitment:

Veterans with ALS will be recruited from the multidisciplinary ALS clinic at the James J. Peters VA Medical Center, Bronx, NY. After our ALS veteran population has been given first option to participate, eligible non-veterans with ALS will be permitted to participate. This will allow for a larger pool of subjects, and will help to ensure balanced allocation among treatment groups. Individuals who indicate desire to participate in clinical research will be referred from colleagues at ALS clinics at New York-Presbyterian Hospital and Mount Sinai Health System. We will not contact anyone unless referring physicians provide assurance that the individual would be interested in receiving further information about this study. Individuals who contact us through online postings at clinicaltrials.gov, which are distributed by various ALS online communities, will also have the opportunity to participate. Participants will be recruited without regard to gender, racial, or ethnic status. We will not contact any patients unless referring physicians provide us with assurance that the patient would be interested in receiving further information about this study.

Eligibility Screening:

Persons interested in participating will be assigned a number beginning at 1. To determine eligibility, interested participants will be asked the “yes” or “no” questions listed below. Persons who answer “no” to any of the following questions will not be eligible for the study:

- Do you have amyotrophic lateral sclerosis, or are you an able-bodied volunteer?
- Are you between the ages of 21 to 75 years?

If the potential participant answers “yes” to all questions, then the informed consent process will continue by inviting the participant for an in-person interview.

Enrollment:

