Aim 1 data analysis: Peak-to-peak amplitude (or F-wave persistence) of conditioned pulses will be normalized to that of unconditioned pulses. For each interaction paradigm, repeated-measure analysis of variance (ANOVA) with factors of subject group, conditioning stimulus intensity, interstimulus interval, and muscle will be performed. Post hoc pairwise comparisons will be made using Tukey's method.

Aim 1 Timeline:

Each subject will undergo two testing sessions on separate days, with a minimum of 24 hours and a maximum of two weeks between visits. Per subject, Aim 1 participation would therefore take 2 to 15 days. 27 subjects will be enrolled, resulting in 54 total testing sessions. A very conservative projection of completing 1.5 testing sessions per week would result in a timeline of 36 weeks or 9 months for completing Aim 1, not including recruitment.

Aim 2: Determine optimal CES parameters for acutely facilitating concurrent arm and hand movements.

Volitional limb movements depend on the same corticospinal and spinal motor circuits as those activated by TMS and F-waves. Therefore, since preliminary data shows that subthreshold CES facilitates TMS responses, CES may also be able to facilitate volitional limb movements. The experiments in Aim 2 will shed light on this clinically applicable question.

Volitional motor tasks: Maximal voluntary effort will be defined as the largest response from 3 attempts prior to testing. Effort will be measured using a customized dynamometer or the root mean square (RMS) of electromyographic activity in the target muscles. The tasks are: thumb-third finger opposition (C8-T1 levels), or wrist extension by extending the dorsal hand laterally against a mounted load cell (C6 level). A combined finger opposition/wrist extension task will also be tested. Subjects will be instructed to perform tasks at target effort levels based on real-time display of ongoing EMG or force output.

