If high-intensity CES inhibits concurrent volitional activity as predicted by Hypothesis 2.2, this would be analogous to the 'cortical silent period' (CSP) noted when cortical TMS is delivered during volitional contraction^{7,8}. The early phase of CSP (the first 50-75 ms after onset of the cortical motor-evoked potential) is mediated by poorly understood spinal mechanisms⁷. Our observations of the onset and duration of a 'spinal silent period' (SSP) in response to CES would shed mechanistic light on this phenomenon.

Aim 2 Data analysis: Rather than peak-to-peak amplitude, the effects of CES on concurrent volitional muscle contraction will be measured using RMS. RMS in 25 ms bins over the 200 ms following each CES pulse will be normalized to the baseline RMS during the 100 ms prior to each pulse. Repeated-measure analysis of variance (ANOVA) with factors of subject group, volitional effort intensity, CES intensity, post-stimulus timebin, and muscle will be performed. Post hoc pairwise comparisons will be made using Tukey's method.

Aim 2 Timeline:

Each subject will undergo two testing sessions on separate days, with a minimum of 24 hours and a maximum of two weeks between visits. Per subject, Aim 2 participation would therefore take 2 to 15 days. 24 subjects will be enrolled, resulting in 48 total testing sessions. A very conservative projection of completing 1.5 testing sessions per week would result in a timeline of 32 weeks or 8 months for completing Aim 2, not including results processing/dissemination.

4. Possible RISKS and protective actions

For subjects with ALS, there is a risk of falling during transfers between different testing positions. To minimize this risk, a clinician will be at the participant's side at all times to assess comfort and provide manual assistance/stabilization as necessary.

The surface electromyography recording and stimulating electrodes and tape have adhesive backing. Therefore, minimal risks such as transient skin irritation at the sites of surface electrode application may occur. Areas with excessive hair will be shaved prior to adhesive application.

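### The ALS versus non-disabled factor in both ANOVAs has no age term and controls are not age-matched, so the group main effect can show an age difference as an ALS effect

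*Combined protocol and SAP*

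**What the plan says.** Section 3 sets the sample at "n=24 subjects with ALS. n=27 non-disabled volunteers". Under Inclusion criteria, non-disabled participants must meet "Age between 21 and 75 years; n=15 for Aim 1, n=12 for Aim 2" and "No known central or peripheral neurological disease or injury". The matching entry for ALS is "Age between 21 and 75 years; n=12 for Aims 1 and 2". The age limits are therefore identical in the two groups, and no age or sex matching is described. The Recruitment paragraph names sources for people with ALS only, and adds: "Participants will be recruited without regard to gender, racial, or ethnic status".

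For Aim 1 the analysis is a "repeated-measure analysis of variance (ANOVA) with factors of subject group, conditioning stimulus intensity, interstimulus interval, and muscle will be performed". For Aim 2 it is the same type of model with "factors of subject group, volitional effort intensity, CES intensity, post-stimulus timebin, and muscle will be performed". Tukey comparisons follow in both aims. Group is in both models; every other listed factor is a stimulus, effort, time or muscle factor. No age or sex covariate, stratification or sensitivity analysis is given.

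The outcomes are ratios within a participant: conditioned to unconditioned response in Aim 1, and post-pulse to pre-pulse RMS in Aim 2. The Enrollment paragraph describes the study as observational.

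**The concern.** Group here is disease status, so nothing in the design balances age between the groups. Shared limits of 21 and 75 bound the ages across a 54-year span (75 - 21) without making the two distributions alike. ALS participants come from ALS clinics and online ALS communities. The source of the non-disabled volunteers is not stated, so their age profile cannot be anticipated.

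If the groups turn out to differ in age, and the degree of facilitation or inhibition by CES varies with age, a model with a group term and no age term assigns that variation to ALS. What is at stake is any statement that people with ALS respond to CES differently from non-disabled people. The plan puts group in both models, so such a statement is a foreseeable product of the analysis.

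**Working it through.** **Counts.** The plan states no power, alpha or effect size for the group comparison, so there is no power figure to reproduce. The counts agree. Controls: 15 + 12 = 27. ALS: 12 + 12 = 24, reading the ALS entry as 12 per aim. Aim 1: 15 + 12 = 27 participants. Aim 2: 12 + 12 = 24. These match both Timeline paragraphs.

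**Form of the test.** In a balanced repeated-measures ANOVA the between-participant group test is equivalent to a two-sample t test on participant means. Its degrees of freedom are 27 - 2 = 25 in Aim 1 and 24 - 2 = 22 in Aim 2.

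**Assumptions, none from the documents.** Two-sided 5% level; no true ALS effect; within-group age SD 14 years; mean age gap 0 to 15 years; within-group correlation r between age and the participant's mean normalised outcome of 0.2 to 0.4.

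**Formulas.**
- Spurious shift in outcome SDs: d = r x gap / 14.
- Noncentrality: d x sqrt(n1 n2 / (n1 + n2)). The multiplier is sqrt(180/27) = 2.582 for 12 v 15 and sqrt(144/24) = 2.449 for 12 v 12.
- The false-positive rate is the two-sided tail of the noncentral t distribution.

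| Gap (years) | r | Shift (SD) | 12 v 15 | 12 v 12 |
|---|---|---|---|---|
| 0 | any | 0 | 5.0% | 5.0% |
| 5 | 0.2 | 0.07 | 5.4% | 5.3% |
| 10 | 0.2 | 0.14 | 6.5% | 6.3% |
| 15 | 0.4 | 0.43 | 18.6% | 17.1% |

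For the last row, d = 0.4 x 15/14 = 0.43, and the noncentralities are 1.11 and 1.05.

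**Scale.** With 80% power at two-sided 5% (also assumed), the detectable group difference is about 1.13 SD in Aim 1 and 1.20 SD in Aim 2. The largest shift in the table is 0.43/1.13 = 38% and 0.43/1.20 = 36% of these.

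**Sensitivity.** A separate simulation with age SD 12 gave, at a 10-year gap and r from 0.2 to 0.5, 6.9-17.8% in Aim 1 and 6.6-16.1% in Aim 2. Larger gaps, which the age limits allow, give higher rates. With no gap, or r = 0, the rate stayed near 5%. With age as a covariate it was 4.8-5.1% in every setting.

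**Interactions.** A group-by-condition interaction compares differences between conditions within participants. An age effect that is the same in every condition cancels from those differences. Simulating the last row of the table for 12 v 15 with such an additive effect, the interaction test rejected 4.9% of the time. Bias there requires that age change the condition effect itself.

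**Cost in precision.** At a fixed age gap, adjustment multiplies the standard error of the group contrast, for the same residual variance, by sqrt(1 + gap^2 x [n1 n2/(n1 + n2)] / [(n1 + n2 - 2) x 14^2]). For 12 v 15 this is sqrt(1 + 100 x 6.667/4900) = 1.07 at 10 years and sqrt(1 + 225 x 6.667/4900) = 1.14 at 15 years. Chance variation in the observed gap raises these to roughly 1.1 and 1.2. Against that, the residual SD falls by a factor of sqrt(1 - r^2), which is 0.98 at r = 0.2 and 0.92 at r = 0.4.

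**The case against.** The strongest reply is that this pilot is not about the group contrast. Hypotheses 1.1 to 1.3, 2.1 and 2.2 all concern what CES does within a participant, each serving as their own control, and none predicts a difference between ALS and non-disabled participants. That stands. A reader might infer that the missing age term undermines the study's main tests; the documents do not support that.

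Normalisation is the second reply, and it stands in part. Age effects that merely scale raw amplitude cancel in the ratios. An age effect on the degree of modulation does not cancel, and that degree is what the ANOVA compares between groups.

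Third, the size rests wholly on assumptions. The documents give no age distribution, no source of controls and no correlation between age and outcome. With a small gap and a weak correlation the inflation is negligible. This also stands, and it is why the result is a range starting at 5%.

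Two further inferences should be resisted. One is that every group interaction is biased; the working shows this needs age to modify the condition effect. The other is that sex confounds the contrast in the same way. The sentence on gender in Recruitment is an equal-access statement, not evidence of imbalance, and no calculation supports a sex effect.

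What survives is narrower. The plan includes group in both models and enrols more controls (27) than people with ALS (24), so a group effect is likely to be reported and read as an effect of ALS.

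**Conclusion.** The concern holds for the group main effect in both aims. As written, the plan cannot separate ALS from age in that contrast, because group is not randomised, controls are not matched and age is in neither model. With an age SD of 14 years, gaps of up to 15 years and correlations of up to 0.4, the false-positive rate of that test lies between 5% and 18.6% in Aim 1 and between 5% and 17.1% in Aim 2. Where in that range the study falls depends on the ages enrolled and on the true age-outcome relation, neither of which is in the documents. The missing age term is certain; its consequence is conditional. Group interactions are exposed only if age modifies the effect of intensity, interval, effort or time bin. The tests of Hypotheses 1.1 to 2.2 are unaffected. The point merits a change to the analysis text but does not threaten the study's core aims.

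**What to change.** Record each participant's exact age. The Eligibility Screening paragraph shows only a yes/no question on the 21-75 range, so this should be confirmed and not assumed.

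In both analysis paragraphs, state that the group contrast will be reported adjusted for continuous age, with the unadjusted result beside it. Wherever a group-by-condition interaction is to be interpreted, add the corresponding age-by-condition term, since an age main effect alone does not protect the interaction. Include sex only as a sensitivity analysis, if numbers allow.

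Frequency-matching controls to the ALS age distribution is optional. It narrows the gap at enrolment and so loses less precision than adjustment alone.

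The cost is a sentence or two per aim, one between-participant degree of freedom for age (two with sex) out of 25 or 22, and a group-contrast standard error about 1.1 to 1.2 times wider at a 10-15 year gap, partly offset by lower residual variance. No extra visits or procedures are needed.

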a secured desktop computer for future analysis using LabVIEW graphical software for instrumentation (National Instruments, Austin, TX, USA). Beat-to-beat finger BP will be monitored using photoplethysmography for assessment of BP variability and baroreceptor reflex activity (CNSystems Medizintechnik; Graz, Austria; # CNAP Monitor 500). Impedance plethysmography will be used to monitor respiration rate (Biopac Systems, Inc.; Goleta, CA.; # RSP100C). These data will be viewed in real time and stored on a secured desktop computer for future analysis using LabVIEW.

Timing: Peripheral motor conduction time is calculated using F-wave and M-wave latencies using the formula $(\text{Latency}_M + \text{Latency}_F - 1) \div 2^{82}$. Central motor conduction time is calculated as the TMS-evoked potential latency minus the peripheral conduction time. These values are used to precisely synchronize arriving TMS, CES, and peripheral pulses at cervical motor neurons in the relevant experiments.

Replication: For Aim 1, testing will occur over three sessions. For Aim 2, testing will occur over two sessions. This will allow confirmation of key intensity and timing parameters defined for each subject over different sessions, improving reliability of the findings.

Aim 1: Map the circuit and synaptic targets of cervical electrical stimulation (CES).

This Aim investigates fundamental CES mechanisms using a classic conditioning-test stimulus paradigm. An electrical conditioning stimulus will be paired within 0-300 ms of a test stimulus delivered at a range of intensities and sites. This will shed insight into which circuits CES activates, and how CES circuits interact with inhibitory and facilitatory endogenous neural feedback pathways.

CES-TMS interactions:

- Hypothesis 1.1: Conditioning subthreshold CES will potentiate spinal motor neuron responses to test TMS pulses.
- Methods: Test TMS pulse intensity will be set at 120% of motor threshold (or 80-90% of maximal stimulator output if threshold not detectable). Conditioning CES pulse intensity will be set between 30-95% of CES motor threshold. For conditioning CES, either single or “theta bursts” (3 pulses at 50 Hz)⁴⁸ will be delivered. All pulse combinations will be delivered at a rate of 0.1 Hz, in pseudorandom parameter order, until 8 responses per parameter have been recorded.

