- Interpretation: Depending on the timing of the observed effect, this would support either the mechanism of heterosynaptic summation between segmental Ia input and descending corticospinal input (facilitation expected to occur at ISI between 2-15 ms)¹, or sensory cortical facilitation of motor cortex excitability (facilitation expected to occur at ISI between 20-60 ms²⁻⁴). This would also set the basis for using subthreshold CES to facilitate spinal cord motor responses during physical training (see Aim 2).

CES-peripheral nerve interactions:

- Hypothesis 1.2: Conditioning CES will increase persistence of F-responses (per 20 stimuli) to retrograde stimulation over the median or ulnar nerve.
- Hypothesis 1.3: Conditioning CES will reduce amplitude of median (flexor carpi radialis) H-responses.
- Speculative hypothesis 1.2: Conditioning suprathreshold CES will block spinal motor neuron F-responses delivered up to 10 ms later.
- Methods: If obtainable, F-wave pulse intensity will be ~110% of the intensity that results in maximal compound motor action potential (CMAP). H-reflex pulse intensity will be calibrated for amplitude ~20-25% of maximal CMAP⁸¹. Conditioning CES pulse intensity will be set between 30-175% of motor threshold. For subthreshold conditioning CES, either single or “theta bursts” (3 pulses at 50 Hz)⁴⁸ will be delivered. All pulse combinations will be delivered at a rate of 0.1 Hz, in pseudorandom parameter order, until 8 (CES-H combinations) or 20 (CES-F combinations) responses per parameter have been recorded.
- Interpretation: Hypothesis 1.2 would indicate that CES positively modulates motor neuron excitability at the spinal level; Hypothesis 1.3 would indicate that CES traveling via sensory afferents homosynaptically depresses ensuing H-reflexes⁶. This would demonstrate the potential for CES to reduce hyperactive muscle stretch responses (spasticity) via segmental interactions^{5,6}; ; and speculative hypothesis 1.2 would demonstrate that high-intensity CES pulses traveling anterogradely via efferent nerve roots collide with retrogradely traveling F-waves.

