CES-motor task interaction: While performing volitional motor tasks at 100%, 50%, or 15-20% of maximal effort, conditioning CES (or sham) pulses will be delivered at a range of intensities between 30%-175% of resting motor threshold. For subthreshold CES, either single or "theta bursts" (3 pulses at 50 Hz)⁴⁸ will be delivered. The effect of CES pulses on RMS electromyographic activity over the subsequent 200 ms will be measured at several different arm and hand muscles and divided by the baseline RMS from the preceding 100 ms. At least 10 seconds will elapse between each CES/motor task combination. Effort level and CES pulse parameters will be varied in pseudorandom order, until 8 responses per parameter have been recorded.

Aim 2 Outcomes:

- Facilitation: At each muscle, the effect of CES pulses on RMS electromyographic activity over the subsequent 200 ms (in 25 ms bins) will be measured and normalized to the baseline RMS from the preceding 100 ms.
- Silent period: At each muscle, the duration of electromyographic silence is measured from the end of the CES-evoked potential until the resumption of volitional muscle activity (defined as mean rectified EMG amplitude less than or greater than mean baseline activity + 2 standard deviations⁸³, respectively).

Hypothesis 2.1: Subthreshold CES will *facilitate* concurrent wrist and hand muscle activation.

Hypothesis 2.2: High-intensity CES will transiently *inhibit* concurrent wrist and hand muscle activation.

Interpretation: Confirmation of Hypothesis 2.1 would substantiate the findings of Hypotheses 1.1 and 1.2 and our updated preliminary data that indicate CES's ability to positively modulate corticospinal and/or motor neuron excitability. We expect optimal facilitation when subthreshold CES is delivered at closer to motor threshold intensity. We do not know whether the effects will differ depending on intensity of volitional effort, but if so, further experiments could investigate the roles played by peripheral, spinal, and supraspinal components of effort intensity⁸⁴. Most importantly, confirmation of Hypothesis 2.1 would represent an

opportunity to directly translate and test this paradigm for lasting clinical benefit by combining repetitive subthreshold CES with repetitive task-oriented physical exercise training in a subsequent study.

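### Pulse pattern is missing from both ANOVAs and task from the Aim 2 ANOVA, and the interval rule that assigns mechanism cannot be read for part of the burst data

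*Combined protocol and SAP*

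**What the plan says.** All places are in Section 3 of the combined protocol and SAP.

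- **CES-TMS interactions, Methods:** "For conditioning CES, either single or" bursts of "3 pulses at 50 Hz" will be given. Conditioning intensity is 30-95% of motor threshold, so all of it is subthreshold.
- **CES-peripheral nerve interactions, Methods:** the same choice, limited to subthreshold pulses ("For subthreshold conditioning CES, either single or" bursts), although intensity runs over 30-175% of threshold. **CES-motor task interaction** (Aim 2) has the same restriction and the same intensity range.
- **CES-TMS interactions, Interpretation:** mechanism is read from the interstimulus interval (ISI). For spinal heterosynaptic summation the text has "facilitation expected to occur at ISI between 2-15 ms"; for sensory cortical facilitation, "facilitation expected to occur at ISI between 20-60 ms".
- **Aim 1 data analysis:** for each interaction paradigm, a "repeated-measure analysis of variance (ANOVA) with factors of subject group, conditioning stimulus intensity, interstimulus interval, and muscle will be performed".
- **Volitional motor tasks:** finger opposition and wrist extension, and then "A combined finger opposition/wrist extension task will also be tested".
- **CES-motor task interaction and Aim 2 Data analysis:** RMS EMG in the 200 ms after a pulse, in 25 ms bins, is "divided by the baseline RMS from the preceding 100 ms". The ANOVA factors are group, effort, CES intensity, time bin and muscle.

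Nothing states which pulse of a burst sets the ISI or time zero, or that single-pulse and burst data are analysed apart.

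**The concern.** Pattern and task are conditions the experimenter sets, yet the listed models have no term for them. A cell at a given intensity and ISI would then average single-pulse and burst responses. Aim 2 is meant to find the best CES parameters for facilitating movement, and a model without pattern cannot compare the two patterns on offer.

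Where bursts are subthreshold only, pooling has a second effect. Subthreshold cells may mix both patterns while suprathreshold cells hold single pulses only, so a contrast across threshold is partly a contrast of patterns.

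The mechanistic reading of Hypothesis 1.1 depends on where in the ISI range facilitation appears. That works when one conditioning pulse precedes the test pulse by one interval. A burst supplies three intervals at once. If some lie in the spinal range and others in the cortical range, facilitation in that cell cannot be assigned to either mechanism by the stated rule.

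**Working it through.** The plan gives no figure of its own on this point, so there is none to reproduce. The check compares conditions with factor lists and then works out the burst timing.

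**1. Conditions against factors**

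| Experiment | Set by the experimenter | In the ANOVA list? |
|---|---|---|
| Aim 1, CES-TMS | Pattern (single, burst) | No |
| Aim 1, peripheral nerve | Pattern, subthreshold only | No |
| Aim 2 | Pattern, subthreshold only | No |
| Aim 2 | Task (3 levels) | No |

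In Aim 2 up to 2 patterns × 3 tasks = 6 combinations share one subthreshold cell. Muscle does not stand in for task, because several muscles are measured during the contractions.

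**2. Burst geometry**

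Spacing = 1000 ms / 50 = 20 ms. Span of three pulses = 2 × 20 = 40 ms. Gap between the two mechanism windows = 20 − 15 = 5 ms.

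**3. Pulse-to-test intervals under each possible ISI reference**

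A negative interval means the pulse comes after the test pulse.

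- *Last pulse, ISI = L:* intervals are L, L+20 and L+40. For L = 2-15 ms they are 2-15, 22-35 and 42-55 ms, so two pulses lie in the cortical window at every such L. For L = 20-60 ms the smallest interval is 20 ms, so none lies in 2-15 ms.
- *First pulse, ISI = F:* intervals are F, F−20 and F−40. For F = 22-35 ms the second pulse is at 2-15 ms. For F = 42-55 ms the third pulse is at 2-15 ms. Affected length = 13 + 13 = 26 of the 40 ms in the long window. For F = 2-15 ms the second and third pulses are at −18 to −5 and −38 to −25 ms.
- *Middle pulse, ISI = M:* intervals are M+20, M and M−20. Both windows are occupied at every M of 2-15 ms (22-35 and 2-15 ms) and at M = 22-35 ms (third pulse at 2-15 ms).

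Each reference therefore leaves a range of burst ISIs with pulses in both windows, but the range differs. With a single pulse there is one interval, and it cannot lie in both windows.

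**4. Aim 2 time zero**

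- *Zero at the first pulse:* pulses at 0, 20 and 40 ms. The second falls in the 0-25 ms bin and the third in the 25-50 ms bin.
- *Zero at the last pulse:* pulses at −40, −20 and 0 ms. Two fall in the 100 ms baseline, and the final 40 of its 100 ms follow the start of stimulation.

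The Aim 2 Data analysis text refers to the periods before and after each pulse, which does not settle the choice for a burst.

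**The case against.** A reader might infer that the spinal-versus-cortical question is lost for every burst cell, or for Hypothesis 1.1 as a whole. The documents do not support that. With last-pulse timing, burst ISIs of 20 ms or more put no pulse in 2-15 ms, and single-pulse cells can answer the question alone. Nor does the overlap fall at fixed ISIs, since it depends on a reference pulse the plan leaves open.

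A reader might also infer that the plan states it will pool. It does not; pooling follows from the factor lists. The choice of pattern could mean one pattern per subject or experiment, and an analysis for each interaction paradigm could mean separate single and burst analyses. In Aim 2 only effort and pulse parameters are said to vary in pseudorandom order, which fits tasks run in separate blocks. These readings are open, but none is stated. If pattern were chosen per subject, it would be an uncontrolled between-subject difference.

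An ISI contrast might also rescue short-interval bursts. A burst with last-pulse ISI of 22-35 ms has pulses at 22-35, 42-55 and 62-75 ms: the same two cortical-window pulses as one at 2-15 ms, without the short-interval pulse. That needs both ISIs on a grid the plan does not give, and roughly additive effects. It is possible, but not a basis for the stated rule.

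Finally, this is a mechanistic pilot with no clinical decision rule. That limits the consequences but leaves the gap in place.

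**Conclusion.** The point holds in a bounded form. Pattern is absent from both factor lists and task from the Aim 2 list, so the models as written cannot show which pattern or task produces facilitation. The interval rule is uninterpretable for part of the burst data: all last-pulse ISIs of 2-15 ms, or first-pulse ISIs of 22-35 and 42-55 ms. Single-pulse cells, and bursts with last-pulse ISI of 20 ms or more, have no competing short-window pulse. In Aim 2, burst stimulation enters the first two outcome bins or the baseline, depending on time zero.

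This rests on the factor lists being complete and on no separate analyses being intended. The timing result needs only the 50 Hz rate, the three pulses and the plan's own windows. The bias from pooling cannot be sized, because the documents give no effects by pattern. Their reports of a spinal pulse inhibiting another 20-50 ms later make a difference plausible, since burst pulses are 20 and 40 ms apart. Those reports concern low suprathreshold pulses, though, and the bursts are subthreshold.

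**What to change.** 1. Base the spinal-versus-cortical inference for Hypothesis 1.1 on single-pulse cells.
2. Add pattern as a factor in the Aim 1 CES-TMS model, where all conditioning is subthreshold and pattern can be crossed with intensity. In the peripheral-nerve experiments and Aim 2 it cannot be fully crossed, so put it in a subthreshold-only or nested model, or analyse bursts separately.
3. Add task as a factor in Aim 2, or analyse by task.
4. Define burst ISI from the last pulse. An ISI recorded from the first pulse converts by subtracting 40 ms; cells where the result is negative have a burst pulse after the test pulse and should be identified as such.
5. For Aim 2 bursts, take the 100 ms baseline before the first pulse, state one time zero, and flag or exclude bins that contain later burst pulses.

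The cost is fewer observations per cell and some precision. For example, if the 8 responses are collected for each pattern, a pooled cell holds 2 × 8 = 16 and a separated one 8. Excluding bins also gives up some early burst response. Stimulation and data collection do not change. The choices should be written down before the data are examined, so that pattern and ISI reference are not picked by result.
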